Non-Damaging Photothermal Therapy of Non-exudative Age
Related Macular Degeneration

Study Protocol and Statistical Analysis Plan
NCT02569892

August 15, 2018

Title:

Non-Damaging Photothermal Therapy of Non-exudative Age Related Macular Degeneration

Introduction

Age Related Macular Degeneration (AMD) is the leading cause of blindness and visual disability among patients exceeding 60 years of age in the western hemisphere. The clinical presentation of AMD ranges from soft drusen in patients with normal visual acuity to geographic atrophy or subfoveal choroidal neovascularization (CNVs), disciform scarring and eventually legal blindness.¹

Approximately 10 to 15% of patients with AMD develop severe visual loss due to geographic atrophy characterized by the atrophy of retinal pigment epithelium, choriocapillaris and outer retina or due to exudative AMD. Nonexudative AMD is responsible for about 25% of the severe visual loss and the remaining is caused by neovascular AMD². Fortunately, with the introduction of pharmacological anti-VEGF treatments to neovascular AMD, exudative AMD can be effectively treated, thereby maintaining good visual acuity for extended period of time. However, there is still no treatment for nonexudative AMD other than vitamin supplementation, and patients inevitably progress to advanced disease and associated visual loss.³

The cumulative incidence of new exudative or atrophic lesions in eyes initially free of advanced AMD has been estimated as 8.6% at one year, 16.4% at two years and 23.5% at three years.⁴ The five-year risk of CNV occurrence in the fellow eye of patients who have already experienced CNV in the first eye, varies from 7% to 87% depending on the coexistence of four main risk factors (presence of five or more drusen, focal hyperpigmentation, one or more large drusen and systemic hypertension).

Owing to the risk of vision loss associated with the presence of large volume of drusen, retinal laser treatment was proposed to prevent progression to advanced AMD. Several clinical trials have been conducted to test the effect of laser photocoagulation on reabsorption of drusen in the macula.⁵⁻¹² Laser burns were applied to the retina, either directly to the drusen or following predefined patterns. Argon, krypton, dye or diode lasers have been used with varying levels of energy (ranging from sub-visible to faint or intense whitish retinal lesions). The assumption was that phagocytic cells or macrophages clearing the laser-induced debris in the retina, RPE and choroid could also reduce or eliminate the drusen. It was also speculated that laser could trigger release of cytokines and growth factors from the RPE, which may act on drusen regression.

A systematic review of all clinical trials using laser treatment of drusen demonstrated that there was a significant reduction of drusen over time. However there was also found a slight increase in the incidence of CNV and geographic atrophy, albeit not statistically significant³. This increase could be related to the fact that conventional photocoagulation used in most of these trials damaged the Bruch's membrane, consequently inducing CNV. Therefore, a non-damaging laser treatment strategy might be able to induce drusen regression without the known side effects of photocoagulation. This hypothesis is supported by the fact that "subthreshold" laser treatments of the drusen resulted in their reduction with much fewer side effects than with

conventional visible burns: 6 out of 63 eyes treated with visible burns developed CNV within 3 months of treatment, while no such CNV was reported for subthreshold treatment. Despite the drusen reduction, the treatment did not slow the progression to geographic atrophy or to CNV, compared to observation in this trial. This might be due to very small number (a few tens) of laser spots applied to the macula. Our approach might rectify this deficiency by applying higher density of the treatment: 500 non-damaging spots.¹¹⁻¹²

Micropulse laser photocoagulation avoids the excessive heating which causes visible burns, tissue necrosis, and related collateral effects¹³, while providing similar clinical benefits as conventional laser coagulation.¹⁴⁻¹⁹ However, the lack of a reliable titration for every patient and absence of visible endpoint makes it difficult for the physician to (a) know which retinal areas have been treated and (b) to ensure the adequate amount of laser energy in the treatment. In addition, the dense coverage of the retina with the sub-visible laser exposures typically requires more than 500 spots in the macula, which is difficult to accomplish without pattern scanning laser. These issues prevented acceptance of this technology in clinical practice.

We have developed the titration protocol for PASCAL laser, which ensures that pulse energy is within the range of clinical efficacy, but does not exceed the tissue damage threshold²¹ in every patient. This protocol, called EndPoint Management, has been recently tested in a clinical trial, which demonstrated its safety and efficacy in treatment of Central Serous Retinopathy²² using 30% energy settings. The trial demonstrated lack of tissue damage and excellent tissue response to the treatment, even after multiple retreatments. The average retreatment period in this trial was found to be 6 months.

We propose to use the same laser parameters for treatment of the macula in patients with early AMD to prevent drusen growth and advancement of the disease into geographic atrophy or neovascularization.

AIMS OF THE STUDY

1. To determine whether photothermal therapy (PTT) of the macula with EpM® reduces the volume of drusen in the macula.
2. To determine whether PTT decreases the incidence of advanced AMD (neovascular AMD or geographic atrophy).

The primary efficacy outcome measure will be the reduction in drusen volume in the central 3mm circle over 12, 18, 24 months in subjects treated with PTT, compared to observation alone.

The secondary efficacy outcomes after the month 12, 18, 24 of follow up will be:

- **Functional outcome:**
 - Mean change in visual acuity in both groups.
- **Anatomical outcome:**
 - Reduction of drusen growth;
 - Prevention of neovascular AMD;
 - Prevention of geographic atrophy based on OCT and FAF.

- **Safety Assessments.** Safety of the treatment will be assessed for ocular adverse event incidence (AEs) and serious AEs (SAEs), based on the reports of the patients and examination during or between visits until the month 24 of follow up. After 24 months, subjects will then be followed for an additional 3 years for observation
- **Serious adverse events (SAEs)** will be monitored continuously.

STUDY METHODS

Design:

- Prospective, Randomized Clinical Trial (RCT).
- 24 months with an additional 3 year observation follow up period. Subjects will be seen once a year and undergo non-invasive testing.
- Total patient recruitment 56 patients.
- Number of arms: 2 arms.
- Number of patients: 28 patients in each arm.

Patient Recruitment

1. Initial Assessment

The study will enroll 56 eyes in total. Patients will be initially assessed as part of their standard management and, if fulfilling all the inclusion criteria, will be referred to a Study Investigator.

At the initial assessment, the investigator will confirm that the patient has satisfied the eligibility criteria stated in the Study Protocol (SPR) and the study will be discussed in full with the study participant (SP). If interested in participating, the SP will be given a written informed consent to take home for further consideration. The patient will have a minimum of 24 hours to decide whether or not to take part in the study. All study procedures, will be explained to the SP by the investigator or staff member. The nature of the study will be also explained to the SP together with hazards of the study procedures, including any possible adverse events. The SP will be informed that he or she is free to terminate participation in the study for any reason.

Any patient unwilling to participate at this stage will be managed as part of the appropriate routine eye care pathway.

The study patient will undergo the Examination Procedures at the Baseline visit. The data from these tests will be used for study data analysis.

2. Examination Procedures at Baseline and Follow-up visits

- (1) ETDRS best corrected visual acuity.
- (2) Slit lamp biomicroscopy: dilated fundus examination with 78D Volk lens, intraocular pressure by Goldmann applanation tonometry.
- (3) Spectral domain OCT (Cirrus SD-OCT): Macular/macular cube/Volume scan & average central retina thickness and Drusen volume.
- (4) Fundus photography and autofluorescence.

The treatment will be randomised at this stage, and the SP will be allocated to arm A (treat) or arm B (observe). The 56 eyes will be randomly allocated to each of the two study arms, 28 in each arm. The SP will be given a trial number, and the treatment record will be coded. **For patients where both eyes meet eligibility criteria both eyes will be enrolled with the Right Eye randomly assigned to active treatment arm or sham arm, with the Left Eye assigned to the opposite arm.**

3. Treatment Visit:

The SP will undergo treatment within 14 days after the examinations are performed.

Patient-eligibility

Inclusion criteria:

1. Older than 60 years of age.
2. Male or female patients with nonexudative AMD with a drusen volume of at least 0.03mm³ on OCT within the central 3mm circle centered on the fovea.
3. Adequate pupil dilatation and clear media to perform color, red-free imaging, fundus autofluorescence imaging, and OCT imaging.
4. Able to give an informed consent.

Exclusion criteria:

1. Presence of signs of advanced AMD, such as CNV, haemorrhages or macular atrophy based on OCT and FAF.
2. Previous macular laser treatment.
3. Any previous ocular condition that may be associated with a risk of developing macular oedema.
4. Vitreomacular traction determined clinically and /or by OCT, which in the opinion of the investigator contributes to the macular oedema (associated or causing a detachment of the fovea).
5. Presence of other macular disease such as epiretinal membrane, macular telangiectasia.
6. Ocular or periocular infections.
7. Planned intra-ocular surgery within one year.
8. Patient is unavailable for follow-up visits.

Study Examination Procedure

Baseline:

1. Full patient history including age, gender, ethnic group, diabetes history, medical history, medication history, ocular history, driving history, smoking status.

Baseline and Follow-up visits (see table):

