At the end of the 24 month period there will be an additional 3 year follow up. During the 3 year follow up, there would be no active component, the subjects will be seen once per year and undergo visual acuity testing and non-invasive retinal imaging to monitor for long term effects of treatment. This should not place a significant burden on the subjects since they are typically seen every 6 to 12 months for routine follow-up.

Best-corrected visual acuity (BCVA) using ETDRS charts at a distance of 4 meters, digital fundus photography, fundus autofluorescence, ocular coherence tomography (OCT), ocular coherence tomography angiography (OCTA when available on the site) will be carried out at baseline and at each follow-up visit.

TEST, treatment	Baseline	0	1 optional	3	6	12	18	24
Laser treatment		x			x	x	x	x
ETDRS visual acuity (BCVA)	x	x	x	x	x	x	x	x
Slitlamp	x	x	x	x	x	x	x	x
OCT	X	X	X	X	X	X	X	X
OCTA*	X	X	X	X	X	X	X	X
Digital Fundus Photography	X	X	X	X	X	X	X	X
Fundus autofluorescence	X	X	X	X	X	X	X	X

*OCTA will be done if available on site

STUDY RANDOMIZATION PROCEDURE

The subjects will be allocated to each arm of the study with simple randomization method using a computer-generated randomization list and sequentially numbered, sealed, opaque envelopes (SNSOE).

After a subject has signed informed consent, their name will be written on the selected envelope by the Clinical Trials Coordinator. The 56 eyes will

be randomly allocated to one of the two arms. The computer randomization will be done by the Clinical Trials Coordinator. The randomization table will be given to an independent person, who will sequentially label 56 envelopes, and enclose the written treatment type within the envelope. The study arm will be coded numerically for each subject.

METHOD OF STATISTICAL ANALYSIS

The data will be analysed using analysis of covariance, adjusting for baseline and disease severity. Results will be presented as differences between the treatment arms with their associated 95% confidence intervals, and non-significant effects interpreted in the context of these and the limited power of the study.

SAMPLE SIZE:

We estimated our sample size based on previous comparable publications that included approximately 50 eyes on average.¹¹⁻¹²

EFFICACY MEASURES:

Primary Outcome:

- Reduction in drusen volume in arm A compared to arm B.

Secondary Outcomes:

- Mean change in visual acuity (ETDRS letters)

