- Mean change in average central retinal thickness (ACRT) after 12, 18, 24 months of follow up.
- The proportion of patients with ACRT < 300 µm on Spectral domain OCT after 12, 18, 24 months of follow up
- Conversion into GA or CNV

SAFETY MEASURES:

- Monitoring of adverse events (AEs) and serious adverse effects (SAEs) (the incidence of ocular AEs and SAEs).
- Assessment of the retinal autofluorescence to identify any laser burn.
- Signs of any laser burn identified at RPE-photoreceptors layers on DRI-OCT.

ADVERSE EFFECTS:

- Any medical incidence in patients who received laser that could be associated with the treatment delivered in the research study.
- Any temporal or transitory adverse effect that has relationship to the study therapy.

REPORTING ADVERSE EVENTS (AE) AND SERIOUS ADVERSE EVENTS

- With any AE, we will treat the SP as appropriate to prevent further complications and to potentially resolve the event.
- SAEs and AE will be reported immediately (when the subject is in the office, if possible or within 24 hours of learning of the event) to the principal investigator, study coordinator and sponsor. The SP subject will be referred for further medical treatment if required.
- Follow-up reports on AEs should indicate whether the AE is presumed to be device-related, or a result of other factors, and should be recorded on the Adverse Events Report. The Adverse Events Report should be completed each time the subject is seen during the management of the incident and at resolution of the incident.
- All AEs occurring from the time of written informed consent throughout the course of the study (end of study is defined as the end of the scan acquisition) will be recorded at the study site.
- The AE should be made to describe it in terms of a diagnosis. If a clear diagnosis has been made, individual signs and symptoms will not be recorded unless they represent atypical or extreme manifestations of the diagnosis, in which case they should be reported as separate events. If a clear diagnosis cannot be established, each sign and symptom must be recorded individually.

All the adverse events shall be recorded in detail as specified below:

Name (Type)	The common name of the adverse event that appeared shall be written down.	
Date of onset	The first date that the physician in charge found the adverse event shall be written down.	

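### The advanced-AMD outcome is combined in Aim 2 but split in the outcome list below it, and ANCOVA is the only method named for a rare yes/no event

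*Combined protocol and SAP*

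**What the plan says.** Aims of the Study gives Aim 2 as "To determine whether PTT decreases the incidence of advanced AMD (neovascular AMD or geographic atrophy"), so either lesion counts. In the same section the secondary outcomes are introduced by "The secondary efficacy outcomes after the month 12, 18, 24 of follow up will be", and the anatomical ones include two separate bullets: "Prevention of neovascular AMD" and "Prevention of geographic atrophy based on OCT and FAF".

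Efficacy Measures, Secondary Outcomes, has one bullet instead: "Conversion into GA or CNV". It carries no visit, although the two retinal-thickness bullets before it do.

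Method of Statistical Analysis covers every outcome in one statement: "The data will be analysed using analysis of covariance, adjusting for baseline and disease severity". It adds "Results will be presented as differences between the treatment arms with their associated 95% confidence intervals", with "non-significant effects interpreted in the context of these and the limited power of the study". No method for a yes/no or time-to-event outcome is named anywhere.

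Exclusion criterion 1 removes eyes that already show advanced AMD. Patient Recruitment allows both eyes of a patient to enter, one in each arm.

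**The concern.** Preventing advanced AMD is one of only two aims. Its outcome appears in two forms, three visits are given without a main one, and the single named method is built for a continuous measurement with a baseline value. Conversion has no usable baseline value, because every study eye starts unconverted. Disease severity could still serve as a covariate.

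What is at stake is the 95% interval that the plan promises to report. With few events, a linear-model interval for a difference in proportions can be too narrow. With no events in either arm its width is zero, which would present a complete lack of information as perfect precision. Splitting the outcome and reading it early both reduce the number of events.

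**Working it through.** The plan has no figure of its own to reproduce here: the 56 eyes rest on the size of earlier studies, with no stated power or event rate.

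**Inputs**
- 28 eyes per arm (Design).
- New exudative or atrophic lesions: 8.6% at one year and 16.4% at two years (Introduction), taken as arm B rates. This is an assumption. No 18-month rate is given, so month 18 was not computed.
- Share of GA and CNV: not given. An even split is assumed, with each eye counted once by its first lesion, and 25/75 as an alternative.
- Risk ratio, arm A to arm B: 0, 0.25, 0.5, 0.75 and 1 (assumed).

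**Expected arm B events**
- Month 12: 28 × 0.086 = 2.4 combined. Each component, at 0.086 / 2 = 4.3%: 28 × 0.043 = 1.2.
- Month 24: 28 × 0.164 = 4.6 combined. Each component, at 0.164 / 2 = 8.2%: 28 × 0.082 = 2.3.

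**Interval tested**

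This is the linear model without covariates and with independent eyes. With observed proportions a (arm A) and b (arm B):
- s² = [28a(1 − a) + 28b(1 − b)] / 54
- interval = (a − b) ± 2.005 × √(2s²/28), where 2.005 is the 97.5% point of t with 54 degrees of freedom.

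Coverage is the total binomial probability of all (arm A, arm B) event counts whose interval contains the true difference, by exact enumeration.

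| Outcome, visit (arm B rate) | RR 0 | RR 0.25 | RR 0.5 | RR 0.75 | RR 1 |
|---|---|---|---|---|---|
| Combined, month 24 (16.4%) | 0.946 | 0.932 | 0.947 | 0.954 | 0.949 |
| Combined, month 12 (8.6%) | 0.917 | 0.914 | 0.909 | 0.943 | 0.951 |
| Separate, month 24 (8.2%) | 0.903 | 0.904 | 0.900 | 0.946 | 0.953 |
| Separate, month 12 (4.3%) | 0.707 | 0.773 | 0.831 | 0.877 | 0.981 |

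**Why the last row is so low**

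The probability of no event in either arm is (1 − pA)^28 × (1 − pB)^28.
- Complete prevention: 0.957^28 = 0.292.
- Halving: 0.957^28 × 0.9785^28 = 0.292 × 0.544 = 0.159.

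So 16% to 29% of trials give a zero-width interval at zero, which misses any real effect.

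**Uneven split**

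At month 24 with a 25/75 split, the components have arm B rates of 0.75 × 16.4% = 12.3% and 0.25 × 16.4% = 4.1%. With halving, coverage is about 95% for the larger and 82% for the smaller.

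**Test size**

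One minus the last column gives 0.051, 0.049, 0.047 and 0.019. The test does not produce excess false positives.

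**Alternative**

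The Miettinen-Nurminen score interval covers 0.949 to 0.996 over the same 20 cells.

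**The case against.** The strongest reply is that the plan largely settles the outcome itself. Aim 2 and Efficacy Measures both word it as combined, as does the background rate in the Introduction, and the two bullets can be read as its components. This stands. A reader might infer that the definition is wholly open until the data are seen, but the documents do not support that: the two bullets are the odd ones out. Nor are visits missing, since the outcome list gives three. What is missing is a main one.

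Second, the plan does not specify the model tested above. It adjusts for disease severity, and its reference to baseline may mean baseline characteristics generally. This also stands, so the coverage figures illustrate the nearest simple reading and do not describe a specified analysis. Covariates cannot rescue a trial with no events, however, because every outcome value is then the same.

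Third, the eyes may be paired. With 28 two-eye patients, a within-patient correlation of 0.2 to 0.4, halving, and the same interval ignoring pairing, simulated coverage is 0.914 to 0.918 (combined, month 12), 0.905 to 0.907 (separate, month 24) and 0.805 falling to 0.774 (separate, month 12). The shortfall remains.

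Fourth, this is a secondary outcome and the plan already concedes "non-significant effects interpreted in the context of these and the limited power of the study". That answers any complaint about power, and none is made here. It does not answer an interval that falls short of its stated level.

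**Conclusion.** The point holds in a limited form. The two-bullet list conflicts with Aim 2 and with Efficacy Measures, no main visit is named, and the only named method suits a rare yes/no event poorly.

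The size depends on the reading. For the combined outcome at month 24, the linear-model interval is acceptable. When conversion is at least halved, the shortfall is small for the combined outcome at month 12 and moderate for the separate outcomes at month 24. It is serious for the separate outcomes at month 12. The figures assume that the Introduction's rates apply, that eyes are independent and that no covariates enter; those for separate outcomes also assume the GA/CNV split. The 25/75 result shows that the separate-outcome shortfall at month 24 can sit almost entirely in the rarer component.

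Two stronger conclusions that a reader might draw are not supported. ANCOVA does not inflate false positives here, since size is 1.9% to 5.1%. And the plan does not break a power promise, because it makes none. This is a correction worth making to a secondary analysis and no threat to the primary comparison.

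**What to change.** - **Outcome.** Align the two bullets under the aims with Aim 2 and Efficacy Measures: the Aim 2 outcome is first GA or CNV by month 24. Report GA and CNV separately as description, with other visits as supporting information.
- **Method.** For this outcome, replace ANCOVA with the difference in proportions and a score-type 95% interval, for example Miettinen-Nurminen, using a version that allows for pairing where both eyes of a patient are enrolled.

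This costs a few sentences and needs no new eyes, visits or data. There are two downsides. Score intervals are wider when events are very few, which is the honest result. A combined outcome can also hide opposite effects on GA and CNV, so the components must still be shown.

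### The total is given as both 56 patients and 56 eyes, which agree only if nobody contributes two eyes, and the planned ANCOVA has no term for the resulting pairs

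*Combined protocol and SAP*

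**What the plan says.** The size appears in two units in the combined protocol and SAP.

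- **Study Methods, Design:** "Total patient recruitment 56 patients", followed by "Number of patients: 28 patients in each arm".
- **Patient Recruitment, Initial Assessment:** "The study will enroll 56 eyes in total".
- **Allocation paragraph, after the list of baseline examinations:** "The 56 eyes will be randomly allocated to each of the two study arms, 28 in each arm". It continues: "For patients where both eyes meet eligibility criteria both eyes will be enrolled". The right eye is randomised, "with the Left Eye assigned to the opposite arm".
- **Study Randomization Procedure:** subjects are said to be allocated, the consenting subject's name goes on an envelope, and an independent person will "sequentially label 56 envelopes". The same paragraph again speaks of 56 eyes.
- **Sample Size:** the only rationale is precedent, publications averaging about 50 eyes.
- **Efficacy Measures:** one secondary outcome is worded per person: "The proportion of patients with ACRT" below 300 µm.
- **Method of Statistical Analysis:** an ANCOVA with baseline and severity as covariates. No unit of analysis and no term for patient or eye pair is given. Non-significant results are to be read through the 95% confidence intervals and the study's limited power.

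**The concern.** A patient with two eligible eyes adds one person and two eyes, so a total in patients and the same total in eyes cannot both be met once such a patient enters. The plan makes enrolling the second eye compulsory and does not say which total governs or how many bilateral patients are expected. The number of people to recruit is therefore open.

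The same rule creates matched pairs across the arms. The analysis section does not mention them. If fellow eyes are analysed as independent, the intervals will not reflect the precision that the design supplies. That matters in a small trial whose null results are to be interpreted through those intervals.

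**Working it through.** **Inputs.** From the plan: 56 patients and 28 patients per arm (Design); 56 eyes and 28 eyes per arm (Initial Assessment and the allocation paragraph); fellow eyes in opposite arms. Not in the plan: the number of bilateral patients b, and the residual between-eye correlation r. Both are assumed below.

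**The plan's own figure.** No effect size, SD or power is given, so 56 cannot be reproduced from a power calculation. The only arithmetic is 28 + 28 = 56. It holds in eyes; in distinct patients it holds only if b = 0.

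**Step 1, totals.** Eyes = patients + b.

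| b | Patients if 56 eyes is fixed (56 − b) | Eyes if 56 patients is fixed (56 + b) |
|---|---|---|
| 0 | 56 | 56 |
| 1 | 55 | 57 |
| 14 | 42 | 70 |
| 28 | 28 | 84 |

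With 56 eyes, b cannot exceed 28, so the number of people lies between 28 and 56.

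**Step 2, per-arm counts.** Under the 56-eye target there are 56 − 2b unilateral patients, half of them in each arm as planned. Patients represented per arm = b + (56 − 2b)/2 = 28 for every b. No patient can put two eyes in one arm, so 28 eyes per arm is also 28 patients per arm. What fails is adding the arms to get 56 distinct people, because the b bilateral patients are counted twice. Under a 56-patient target the per-arm count would instead be b + (56 − b)/2 = 28 + b/2, for example 35 at b = 14. So the Design list's two lines also conflict with each other once b is at least 1.

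**Step 3, precision.** Eyes within an arm come from different people, so the within-arm variance s² is estimated correctly. What an independence analysis omits is the covariance across arms. With n = 28 eyes per arm and p = b/28 the share of eyes that come from pairs:

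- Independence assumed: variance of the arm difference = 2s²/n.
- Pairs recognised: variance = 2s²/n − 2b·r·s²/n² = (2s²/n)(1 − pr).
- Ratio of interval widths = 1/√(1 − pr).

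In units of s, the independence SE is √(2/28) = 0.267.

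| p (b) | r | Correct SE | Width ratio |
|---|---|---|---|
| 0.5 (14) | 0.4 | √(0.0714 × 0.80) = 0.239 | 1/√0.80 = 1.12 |
| 0.5 (14) | 0.6 | √(0.0714 × 0.70) = 0.224 | 1/√0.70 = 1.20 |
| 1.0 (28) | 0.6 | √(0.0714 × 0.40) = 0.169 | 1/√0.40 = 1.58 |

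These are ratios of standard errors and ignore the change in degrees of freedom. At p = 0 or r = 0 the ratio is 1.

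**The case against.** The strongest reply is that the intended target is plain. Eyes are the unit in the recruitment, allocation and randomisation text, and the only sample-size rationale counts eyes. On that reading the Design list has one loose line and nothing in the trial's size changes. The interval question is separate from the wording: changing patients to eyes would not alter it, it depends on assumed p and r, and r is what remains after covariate adjustment, which the plan does not give.

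Most of this stands, and it rules out several stronger readings that a reader might infer:

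- **That 28 patients per arm is meaningless, or the denominators are wrong.** Step 2 shows otherwise under the eye target. The ACRT proportion has a valid denominator in each arm, and an ocular adverse event belongs to an eye and so to an arm. Only non-ocular events in bilateral patients cannot be assigned to an arm.
- **That the trial could run to 112 eyes.** That needs 56 patients, all bilateral, and contradicts every statement made in eyes.
- **That 56 envelopes prove one draw per eye.** The text puts a subject's name on an envelope, which reads as one per subject, and 56 is the most subjects that 56 eyes can need. The gap is only that no instruction says how one envelope serves two eyes.
- **That pairing inflates false positives.** Pairs sit in opposite arms, so ignoring a positive correlation overstates the standard error.

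What does not stand is leaving the text alone. The two totals conflict as soon as b is 1, and the fellow-eye rule plainly anticipates such patients.

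**Conclusion.** The point holds as an inconsistency in the stated total, together with an omission in the analysis. The patient total fails if any bilateral patient is enrolled; for 56 eyes the number of people is 28 to 56, and the documents do not say where in that range it will fall. The count of 28 per arm survives under the eye target as a planned number, although simple randomisation does not guarantee an exact split.

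An ANCOVA that treats all eyes as independent gives intervals too wide by 1/√(1 − pr): about 12%, 20% and 58% in the three cases shown. Those sizes rest on assumed p and r, on equal arms, and on a correlation that is positive after adjustment. The error is conservative. It costs precision and makes a null result look less informative than it is; it does not undermine a positive one.

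**What to change.** 1. Replace the patient total in the Design list with 56 eyes, 28 per arm, from 28 to 56 patients depending on bilateral enrolment, with recruitment ending at 56 eyes.
2. In Study Randomization Procedure, state that a bilateral patient uses one envelope, which sets the right eye's arm and hence the left eye's.
3. Word the ACRT proportion in eyes. Report b, and give both eye and patient counts. List non-ocular events in bilateral patients separately from the arm comparison.
4. In Method of Statistical Analysis, name the eye as the unit and add a patient effect to the ANCOVA, through a mixed model or an equivalent analysis that uses the pairs.

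The cost is protocol wording and a slightly more complex, but standard, model. No additional recruitment is needed. The downside to state openly is that the number of people may be as low as 28, half of what the Design list now announces.
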